## Effect of resveratrol on age-related insulin resistance and inflammation in humans

### OVERVIEW

We hypothesize that resveratrol will improve insulin resistance, tissue lipid accumulation, inflammation, and mitochondrial function in middle aged and Type 2 Diabetes subjects. Using state of the art physiological tools for human investigation, we have shown that adipose tissue inflammation and tissue lipid accumulation are enhanced with aging in concert with systemic insulin resistance. We will administer resveratrol to overweight middle aged humans and study its effects on insulin action, tissue lipid accumulation, inflammation, and mitochondrial function. We will perform paired hyperinsulinemic clamps, the "gold standard" measure of insulin action, following both placebo and resveratrol treatment. We will perform adipose tissue and muscle biopsies to assess inflammatory response in adipocytes and adipose tissue macrophages, and to assess mitochondrial biology in muscle. Noninvasive H magnetic resonance spectroscopy (MRS) will be used to quantify the effects of resveratrol on tissue lipid accumulation.

### SPECIFIC AIMS:

Human aging is associated with increased fat mass, insulin resistance and systemic inflammation. In addition to overall increases in fat mass, accumulation of lipid in such insulin-sensitive tissues as liver and skeletal muscle appears to contribute importantly to insulin resistance. Furthermore, age-related decreases in muscle mitochondrial ATP production rate and mitochondrial DNA copy number are likely to contribute to impaired insulin-mediated glucose disposal, as well as decreased muscular endurance and activity levels. Additionally, systemic inflammation is now believed to contribute to insulin resistance and thus ultimately to many age-related disorders, including diabetes mellitus, Alzheimer's disease, atherosclerosis and many cancers. Recently, it has been recognized that obesity and aging are both associated with increased macrophage infiltration into adipose tissue, and that these infiltrating macrophages are an important source of systemic cytokine production. We have previously reported that adipose macrophages from older humans display increased activation (and production of pro-inflammatory and pro-atherosclerotic peptides). This heightened reactivity of adipose macrophages in older individuals and in those with Type 2 diabetes is likely to contribute both to insulin resistance and to systemic inflammation.

Mammalian Sirt1 seems to be particularly important in regulating glucose homeostasis, insulin action and nutrient sensing. Collectively, several studies have shown that activation of Sirt1 by pharmacological agents like resveratrol has intracellular effects that are strikingly similar to those observed with caloric restriction. Specifically, resveratrol has been shown to improve mitochondrial function and appears to protect against metabolic disease by activating PGC-1alpha. Activation of PPAR-gamma in macrophages by resveratrol reduces activation of these inflammatory cells, which may be very pertinent to adipose tissue inflammation. It has been proposed that resveratrol may improve insulin resistance, although this has yet to be established *in vivo* in animals or humans.

Moreover, resveratrol has been shown to enhance cognitive function, reduce neural degeneration, and improve motor function in animal models. ***Thus, for this project we hypothesize that resveratrol will mediate important metabolic and anti-inflammatory effects that will improve insulin resistance in middle aged and older humans and in those with Type 2 diabetes.*** Specifically, we will determine whether and how Sirt1 activation with resveratrol will impact systemic glucose metabolism, lipotoxicity, mitochondrial dysfunction, inflammation, and motor and cognitive function in insulin resistant humans.

**Aim 1: To study the effects of resveratrol on age and diabetes related insulin resistance.** *We hypothesize that treatment of overweight, middle aged human subjects and those with Type 2 diabetes with resveratrol will result in improved insulin sensitivity, as demonstrated by increased insulin-stimulated glucose uptake and enhanced insulin-mediated suppression of glucose production.* Insulin action will be evaluated by stepped hyperinsulinemic euglycemic insulin „clamp” studies in middle aged subjects with normal glucose tolerance, with progressive increases in insulin levels designed to optimally examine both hepatic and peripheral insulin sensitivity.

**Aim 2: To examine the effects of resveratrol on systemic inflammation and/or on adipose tissue macrophages.** *We hypothesize that treatment of overweight, middle aged human subjects and in those with Type 2 diabetes with resveratrol will lead to reductions in systemic inflammatory markers and reduced content and/or activation of adipose tissue macrophages.* Systemic inflammatory markers to be measured will include TNF-a, IL-6, IL-1b, MCP-1. Adipose tissue macrophages will be isolated from subcutaneous abdominal adipose tissue, and will be quantified by fluorescence activated cell sorting (FACS) analysis. Gene expression of a variety of pro-inflammatory and pro-atherosclerotic factors will be examined by „real-time” rt-PCR, to determine how resveratrol affects activation of adipose macrophages.

**Aim 3: To explore the effects of resveratrol on skeletal muscle metabolism and function.** *We hypothesize that resveratrol treatment will enhance mitochondrial metabolism and improve strength and contractility.* In collaboration with the Mitochondrial Metabolic Core and Department of Neurology, we will examine the effects of systemic resveratrol on mitochondrial content, signaling molecules involved in mitochondrial biogenesis, DNA and protein oxidative damage, mitochondrial respiration in human skeletal muscle, and motor function and mobility

**Aim 4: Assess the effects of resveratrol on cognition.** *We hypothesize that resveratrol will enhance cognitive function in middle-aged individuals and in those with Type 2 diabetes.* In collaboration with the Department of Neurology, we will examine cognition, including attention networks of alerting, orienting, and executive attention, as well as perform a clinical neuropsychology battery providing a comprehensive assessment of cognitive function, including measures of: a. intelligence, b. memory, c. language, d. executive function, e. visuospatial function and praxis, f. processing speed, and g. mental status.

**These proposed studies will address several unresolved questions about the role of Sirtuins/Sirt1 in humans:**

1. on insulin sensitivity in liver and in peripheral tissues (particularly skeletal muscle)
2. on several aging-associated determinants of insulin resistance, including:
  - tissue lipid accumulation
  - adipose tissue and systemic inflammation
  - mitochondrial and motor function
  - cognitive function

## BACKGROUND AND SIGNIFICANCE

**The metabolic syndrome of aging and its clinical consequences.** The metabolic syndrome of aging defines a cluster of abnormalities, including insulin resistance, obesity, abnormal glucose tolerance, dyslipidemia, and hypertension (1). Obesity and/or chronic increases in nutrient intake are increasingly recognized to play central roles in the pathogenesis of many age-related diseases, including diabetes mellitus, arteriosclerotic and atherosclerotic vascular diseases, many types of cancer (particularly breast, prostate, colorectal and endometrial), and Alzheimer's disease (2,3). Together, these conditions contribute importantly to the obesity-related increase in all-cause mortality (4,5). Furthermore, the presence of insulin resistance and the „metabolic syndrome“ (impaired glucose tolerance, dyslipidemia, hypertension, visceral obesity, decreased fibrinolysis) is highly correlated with all of these diseases (6,7,8,9,10,11,12).

**Role of aging per se in the pathogenesis of metabolic changes.** It is particularly important to note that aging itself is associated with increases in inflammatory activity (13). Indeed, changes in the innate immune system have been noted with aging (14). In particular, aging is associated with increased circulating levels of cytokines and acute phase proteins *in vivo*, including TNF-alpha and IL-6 (15,16,17,18). The chronic low-grade inflammation in aging and is epidemiologically related to age-associated disorders (eg, Alzheimer disease, atherosclerosis, type 2 diabetes, etc.) and enhanced mortality risk (19,20,21), and adversely impacts hypothalamic pathways vital to energy balance and glucose homeostasis (22). Among the proposed explanations for this phenomenon, which has been referred to as "inflamm-aging," are continuous exposure to antigenic loads and stress (19).

Furthermore, there is a remarkable similarity in pathologic processes between aging and diabetes mellitus, (23). It is especially noteworthy that nondiabetic older individuals can develop microvascular changes, eg. retinopathy (24,25) and neuropathy (26), that are pathologically indistinguishable from those seen in diabetes mellitus (DM). Indeed, both aging and DM are associated with increased availability of certain substrates such as FFA, as well as increased inflammation and altered body composition.

**Effects of aging on mitochondrial function:** Mitochondria are known as the "power plants" of eukaryotic cells, generating most of their adenosine triphosphate (ATP) supply through oxidative phosphorylation and electron transfer (27). They are furthermore involved in a number of other important processes, such as apoptosis, cell signaling, and control of cell growth and differentiation. The master regulator of mitochondrial biogenesis and function has been shown to be peroxisome proliferator-activated receptor  $\gamma$ -coactivator1 $\alpha$  (PGC-1 $\alpha$ ). PGC-1 $\alpha$  induces mitochondria specific transcription factors, such as nuclear respiratory factors (NRFs). NRFs in turn activate mitochondrial transcription factor A (TFAM) and thereby induce mitochondrial (mtDNA) replication (28,29).

With increasing age there appears to be a decline in mitochondrial function and number (30,31,32). In the elderly, declines in mitochondrial transcription levels (30), muscle mitochondrial protein synthesis (33) and, importantly, decreases in key mitochondrial enzymes and maximal ATP production capacity (MAPR) have been observed (30). Since the transcription of nuclear encoded genes of mitochondrial proteins is regulated by PGC-1 $\alpha$  (28), it is possible that the fundamental problem is at the level of nuclear and mitochondrial gene expression. Recent studies have suggested that the underlying cause for mitochondrial dysfunction may be aging-associated reductions in AMP-activated protein kinase (AMPK) activity (34). Activated AMPK phosphorylates and thereby induces PGC-1 $\alpha$  gene expression in skeletal muscle (Jaeger et al. 2007). Lower activity levels with increasing age could furthermore present a decreased stimulus for DNA replication, resulting in reduced mtDNA copy

numbers (35). In support of this, various studies have shown a positive effect of exercise on PGC-1 $\alpha$  expression and mtDNA copy number (31,34,36,37). In particular, exercise is likely to significantly stimulate AMPK activity, and thus PGC-1 $\alpha$  phosphorylation (34).

**Mitochondrial function and insulin action:** There has been increasing evidence suggesting an association between muscle mitochondrial dysfunction and insulin resistance. Mitochondrial oxidative activity and ATP synthesis are both reduced in states of impaired glucose tolerance and insulin resistance. This was seen in a recent study by Petersen et al. (2003) comparing mitochondrial function between healthy, lean, elderly and healthy, lean, younger volunteers (38). Their results showed a ~40% reduction in mitochondrial activity and oxidative phosphorylation in addition to insulin resistance in the elderly subjects compared to the controls. Another study noted reduced mitochondrial activity and increased skeletal muscle triglyceride storage in young insulin-resistant offspring of diabetic parents compared to insulin sensitive controls (39). However, whether the mitochondrial dysfunction is primary or secondary to the pathogenesis of insulin resistance is currently unknown. A number of studies have proposed that muscle mitochondrial dysfunction may play an etiological role in insulin resistance (32,34,40). Reznick et al. reported a strong relationship between insulin resistance, dysregulated intracellular lipid metabolism and age-related reductions in AMPK-activity (34). They suggested that decreased activation of AMPK, and thus PGC-1 $\alpha$ , as well as mitochondrial fatty acid oxidation with aging could lead to mitochondrial dysfunction and increased muscular triglyceride accumulation, thereby predisposing to insulin resistance and type 2 diabetes mellitus (T2DM). Increased intracellular triglyceride storage in liver and skeletal muscle results impairs insulin-stimulated glucose uptake in muscle (41).

An alternative hypothesis is that insulin resistance itself leads to mitochondrial dysfunction with age since insulin resistant states, such as type 2 diabetes mellitus (42), decrease the transcription and translation of mitochondrial proteins (43, 44, 45) and mitochondrial biogenesis in muscle is enhanced by insulin (46). A study by Karakelides et al. recently demonstrated a reduced skeletal muscle mitochondrial ATP production rate (MAPR) and gene transcript levels following insulin deprivation (47). Reduced muscle mitochondrial function may also affect numerous other cellular functions including synthesis of proteins, such as contractile proteins (35,48). Age-related declines in activity levels, ectopic accumulation of fat, and sarcopenia may be related to reduced contractile protein synthesis in combination with decreased ATP production in aging and could result in insulin resistance.

**SIRT1 effects on glucose metabolism and insulin action:** Recent research has found one of the seven sirtuin genes, SIRT1, to impact mitochondrial function and biogenesis through positive regulation of PGC-1 $\alpha$  activity (49,50). SIRT1 is the mammalian homologue of NAD-dependent histone deacetylase Sir2 (silencing information regulator 2) and belongs to the family of proteins collectively known as sirtuins. It is involved in processes such as cell survival, fat metabolism, and insulin and glucose production (51) and has been shown to control the hepatic gluconeogenic/glycolytic pathways in the fasted state through deacetylation of PGC-1 $\alpha$  (50,52). One way in which lifespan can be extended in mammals is through caloric restriction. Aging significantly reduced SIRT1 activity in heart of rats (53). Loss of SIRT1 with age was accelerated in mice with accelerated aging but was not observed in long-lived growth hormone-receptor knockout mice (54). Since Sirt1 expression is induced in multiple tissues including the liver, brain and muscle during periods of caloric restriction, it seems likely that Sirt1 may be a potential candidate for enhancing mammalian longevity.

SIRT1-induced activation of PGC-1 $\alpha$  in cultured liver cells has a differential effect on hepatic glucose production, repressing glycolysis but increasing gluconeogenesis (GNG) (52). By deacetylating forkhead transcription factor FoxO1 in hepatocytes SIRT1 increases the expression of gluconeogenic genes (55). Moreover, the over-expression of pancreatic beta-cell specific SIRT1 in mice has been shown to improve glucose tolerance and increase glucose stimulated insulin secretion, whereas the expression of SIRT1 is decreased in insulin resistant cells and the inhibition of SIRT1 induces insulin

resistance (56,57). In Zucker fa/fa rats, SIRT1 activators were recently shown to improve whole-body glucose homeostasis and insulin sensitivity in adipose tissue, skeletal muscle and liver (58).

SIRT1 exerts numerous additional effects on energy metabolism. It modulates glucose and lipid metabolism through its regulation of the adipocyte-derived hormone adiponectin (51). Adiponectin has been shown to improve insulin sensitivity and may inhibit the development of insulin resistance (59). SIRT1 increases the concentration of adiponectin through deacetylation of FoxO1 $\alpha$  (60). In white adipose tissue, SIRT1 is thought to play a role in adipogenesis by promoting fat mobilization through down-regulation of PGC-1 $\alpha$ , resulting in decreased triglyceride storage and increased secretion of free fatty acids (FFA) (61). SIRT1 may also contribute to the process of inflammation, considering it inhibits the transcription of nuclear factor-kappa B (NF-kappa B), one of the key regulators of inflammation (51). The pro-inflammatory state is one of the characteristics of obesity and the metabolic syndrome (62). *Thus, as SIRT1 is increasingly being recognized as an important regulator of metabolic homeostasis and mitochondrial function, targeting SIRT1 to ameliorate age-related mitochondrial dysfunction and insulin resistance shows great promise.*

**Resveratrol's effects on insulin action and glucose homeostasis:** Resveratrol (3,5,4"-trihydroxystilbene) is a plant derived polyphenolic compound mainly well known for its antioxidant and phytoestrogenic properties and is mainly found in the skin of grapes and in red wine (63). Previous studies have also revealed its anti-tumorigenic and anti-inflammatory qualities (51,63). It has been shown to possess antiplatelet (64,65) and cardioprotective, anti-atherosclerotic effects (66,67). Howitz et al. (2003) demonstrated the ability of resveratrol to significantly increase the activity of SIRT1 through allosteric interaction, resulting in increased PGC-1 $\alpha$  activity (68). Resveratrol has been shown to produce SIRT1-dependent effects in mammalian cells that improve organismal health and cellular function, such as increased insulin sensitivity, mitochondrial number, and improved motor function (49). In a study by Baur et al. (2006) resveratrol was able to prevent the negative effects of excess calorie intake in mice on a high calorie diet (49). In their studies, the physiology of middle-aged mice on a high-calorie diet shifted towards that of mice on a standard diet when treated with resveratrol, significantly increasing their survival. Resveratrol has also been shown to increase mitochondrial biogenesis and oxidative phosphorylation, as well as reduce diet-induced obesity and insulin resistance in a rodent model (50). Furthermore, in streptozotocin-induced diabetic rats, resveratrol treatment improved hyperglycemia, insulin resistance, hypertriglyceridemia, and common diabetic symptoms such as weight loss, polydipsia and polyphagia (69). In conclusion, given the potential of resveratrol, through activation of SIRT1, to positively impact mitochondrial function and metabolic homeostasis, makes it an optimal instrument of investigation in our proposed studies.

**Resveratrol's effects on neural function:** Recently, much attention has been paid to the neuroprotective effects of resveratrol. A number of studies have demonstrated protective effects of SIRT1 activation against amyloid- $\beta$  toxicity in Alzheimer's disease (70,71). Neurodegeneration in the hippocampus was reduced and learning impairment was prevented in a mouse model of Alzheimer's disease when intracerebroventricular resveratrol was given (72). Of note, Alzheimer's disease is associated with impaired mitochondrial energy metabolism (73), and mitochondrial dysfunction in Alzheimer's disease has been shown to be related to age-dependent interactions of amyloid- $\beta$  with mitochondrial proteins (74). SIRT1 expression may activate genes responsible for neuronal protection and protect neurological function in disorders such as seizures and brain ischemia (75,76). Resveratrol has also been shown to prevent diabetes-induced learning and memory impairment, modulate cholinergic neurotransmission, and improve cognition in streptozocin-induced diabetic rats (77). Given the neuroprotective properties of resveratrol in rodent models, it would be intriguing to further investigate these effects in the proposed human studies.

## **Resveratrol in Human Subjects**

### **RATIONALE**

Since a causal link between Sirt1 and aging and diabetes related metabolic changes has not yet been established in humans, this protocol is indispensable to establishing the clinical relevance of this program. Sirt1 shows significant potential as a useful therapeutic target that can be used in ameliorating many of the conditions associated with the metabolic decline of aging and in Type 2 diabetes. We are particularly interested in investigating the role of Sirt1 in the regulation of glucose homeostasis, insulin action and mitochondria function in humans. Furthermore, demonstrating the ability of resveratrol to reverse the metabolic changes of aging and Type 2 diabetes would be of tremendous therapeutic importance, particularly in light of the feasibility and safety of longterm administration of this orally available agent.

Our decision to study middle aged subjects is primarily due to the importance of timing this intervention to decrease aging-related metabolic changes prior to the presentation of serious age-related diseases. An additional advantage is the feasibility of recruiting and studying subjects of this age group with somewhat arduous insulin clamp studies, biopsies and muscle function tests, as compared to a frailer group of elderly subjects. Our preliminary studies, shown below, indicate that individuals above 40 years of age already have substantial age-related declines in insulin sensitivity that would be appropriate targets of intervention. Additionally, since resveratrol appears to exert more beneficial effects in animal models of caloric excess, overweight subjects will be recruited for these studies. Similarly, subjects with Type 2 diabetes have established insulin resistance and nutrient excess as demonstrated by elevated free fatty acids and are likely to benefit from this intervention.

The proposed *in vivo* studies will permit the study of effects on insulin action in concert with effects on adipose macrophage content and activation and muscle function, as well as circulating inflammatory mediators. Such a comprehensive analysis would be necessary to adequately connect the entire hypothesis in humans.

### **EXPERIMENTAL APPROACH AND METHODS:**

#### **STUDY POPULATION AND RECRUITMENT**

Overweight, middle aged and type 2 diabetes subjects will be recruited by a variety of approaches, as described below. Subjects will range in age from 21 to 65 years, will be overweight (BMI 25-30 kg/m^2) with and without diabetes mellitus. All subjects with a history of liver disease or liver abnormalities, hyperlipidemia, hypertension, heart disease, cerebrovascular disease, seizures, bleeding disorders, muscle disease, a known history of ovarian, uterine, breast cancer or smoking will be excluded. The following subjects will also be specifically excluded: mentally disabled persons, prisoners, pregnant women, subjects with a history of ethanol or drug or toxin exposure which could be associated with neuropathy, any subject deemed incapable of giving voluntary informed consent, and subjects with a history of a bleeding disorder or with a prolonged PT or PTT. Furthermore, subjects allergic to Novocain, Benzocaine and Lidocaine will also be excluded. Given potential concerns (based on *in vitro* observations) that resveratrol might inhibit various cytochrome P450 enzymes involved in drug metabolism, use of the following drugs will be exclusionary for this study: anti-coagulant and anti-platelet drugs, anti-epileptics, mexilitene, quinidine, cyclosporine, tacrolimus, and HIV protease inhibitors (see below under Protection of Human Subjects). NSAIDS should be avoided as far as possible during the study period. Additionally, given confounding effects of extreme exercise on muscle triglyceride content, highly trained or professional athletes will be excluded from the studies.

Women in the child-bearing age-group will be allowed to participate in the studies provided that they have negative pregnancy tests within a week of the studies and that they are not breast-feeding. Children below the age of 18 will be excluded from the current protocol, given the use of labeled isotopes. Prior to their enrollment in the study the purpose, nature, risks and benefits of the study will be explained to all subjects and their voluntary, informed, written consent will be obtained. All subjects will have a screening visit to allow for clinical evaluation, including history, physical examination and consent procedures.

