### **General Experimental Conditions:**

On the day of the first pancreatic clamp study the patients will receive a 28 days" supply of resveratrol capsules. The pilot study will be an open-labeled study. The study design requires that all 55 subjects participate in all of the proposed studies, as outlined below. Consequently, additional subjects will be recruited to compensate for those subjects who cannot complete all of the required studies.

Prior to each study, subjects will meet with study personnel to discuss dietary recommendations. Each subject will be instructed to follow a standardized diet plan for three days prior to each of the clamp studies (40% fat: 20% saturated, 10% polyunsaturated, 10% monounsaturated; 35% carbohydrate; 25% protein). Subjects will be asked to refrain from vigorous exercise for three days prior to each clamp study.

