### **Aim 1: To study the effects of resveratrol on age-related insulin resistance**

*We hypothesize that treatment of overweight, middle aged or Type 2 diabetes subjects with resveratrol will result in improved insulin sensitivity, as demonstrated by increased insulin-stimulated glucose uptake and enhanced insulin-mediated suppression of glucose production.*

We will study the following subject group:

- **Overweight and either young or middle aged** (BMI 25-30 kg/m^2, age 21-65) nondiabetic subjects, n=40 diabetic subjects (BMI=25-35) n=15

Each subject will receive a 28 day course of **resveratrol** (n=55). RevGenetics will supply the resveratrol (500 mg capsules; 2 capsules bid) for our proposed studies. A certificate of analysis has been provided by the manufacturer.

A comprehensive study of whole-body insulin action will be undertaken with specially designed „stepped” euglycemic (~90 mg/dl) -hyperinsulinemic clamp studies, both before and after administration of resveratrol.

Thus, we will compare the following parameters under paired conditions in each subject, on day 0 and day 28 of resveratrol treatment:

- a. **hepatic insulin action:** this will be determined as the ability of low infusion rates of insulin (20 mU/m^2.min above basal requirements) to suppress glucose production during the “**low insulin phase**” of the clamp studies.
- b. **peripheral insulin action:** this will be determined as the ability of high infusion rates of insulin (80 mU/m^2.min above basal requirements) to stimulate glucose uptake during the “**high insulin phase**” of the clamp studies.

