### Schedule of proposed clinical studies:

**Day -1:** Subjects visit the Ferkauf School of Psychology at 8 am for motor and cognitive function tests. Subject with type 2 diabetes will present at 2 pm for cognitive and motor testing then be admitted to Weiler Hospital at 5 pm the night before the clamp study.

**Day 0:** Subjects admitted to GCRC at 8 am following a 10 hour fast,

- first stepped insulin clamp study
- fat and muscle biopsies

**Days 1-28:** Subjects receive oral resveratrol (last dose on day of final clamp study)

**Day 27:** Subjects visit the Ferkauf School of Psychology at 8 am for motor and cognitive function tests. Subject with type 2 diabetes will present at 2 pm for cognitive and motor testing then be admitted to Weiler Hospital at 5 pm the night before the study.

**Day 28:** Subjects admitted to GCRC at 8 am following a 10 hour fast

- second stepped insulin clamp study
- fat and muscle biopsies

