## HUMAN SUBJECTS RESEARCH SECTION

### **Protection of Human Subjects**

#### **1. RISKS TO THE SUBJECTS**

##### **Human Subjects Involvement**

Subject involvement will include a preliminary screening visit for history, physical exam and lab testing to determine eligibility. Subsequently, each subject will participate in two infusion studies with frequent blood glucose monitoring.

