##### **Human Subject Characteristics**

The study population will consist of at least 40 nondiabetic subjects and 15 diabetic subjects with the following characteristics: ages 21-65 years, with BMI between 25 and 30 kg/m^2. The following subjects will be specifically excluded: children, mentally disabled persons, prisoners, pregnant women, fetuses, subjects with a history of ethanol or drug or toxin exposure which could be associated with neuropathy, any subject deemed incapable of giving voluntary informed consent, and subjects with a history of a bleeding disorder or with a prolonged PT or PTT; a history of uterine, breast, or ovarian cancer, renal disease, and liver disease or impairment. Women in the child-bearing age-group will be allowed to participate, provided they have negative pregnancy tests. The research topic to be studied is not relevant to the involvement of special classes or groups of subjects and therefore no criteria for their involvement are specified.

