**Early Study Termination:**

Process: The P.I. will determine if the study is to be terminated prior the scheduled study conclusion. Early study termination will be considered in the event of an unanticipated serious adverse event determined to be possibly, probably or definitely related to the study. The P.I. may also terminate the study if a positive drug screening test at any time during the study is found. Payment will be reduced to \$50 and the subject will be withdrawn from the study

Reporting: The P.I. will report the decision to terminate the study to the IRB within 48 hours of this determination. The P.I. will submit a narrative description of the reasons for early termination of the study within 10 days.

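### The protocol body sets no contraception condition and no instruction to stop capsules on pregnancy during 28 days of home resveratrol at 2000 mg/day

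*Combined protocol and SAP*

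**What the plan says.** Study Population and Recruitment lists pregnant women among the exclusions. It lets women of child-bearing age take part "provided that they have negative pregnancy tests within a week of the studies and that they are not breast-feeding". Human Subject Characteristics repeats the exclusion and the test, without a time window: "Women in the child-bearing age-group will be allowed to participate, provided they have negative pregnancy tests". Ages run from 21 to 65, and Inclusion of Women expects half the subjects to be female.

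The treatment is taken at home. Aim 1 specifies "resveratrol (500 mg capsules; 2 capsules bid) for our proposed studies", for 28 days. General Experimental Conditions hands out the whole supply at once: "On the day of the first pancreatic clamp study the patients will receive a 28 days" is how that sentence opens, and it goes on to the capsule supply. The Schedule of proposed clinical studies places dosing on days 1 to 28, between clamps on days 0 and 28.

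The protocol does write rules for the dosing period on other matters. On concomitant drugs: "NSAIDS should be avoided as far as possible during the study period". On drug use: "The P.I. may also terminate the study if a positive drug screening test at any time during the study is found", after which the subject is withdrawn (Early Study Termination). Neither section has a counterpart for pregnancy, and no other section supplies one.

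**The concern.** Pregnancy is an exclusion for the whole study, but the only control on it is a test tied to the clamps. A woman may conceive after day 0, or may be too early in pregnancy on day 0 for a test to show it. Nothing in the protocol body aims to prevent the first case. In both cases nothing says what happens to the capsules she holds once pregnancy is suspected. An investigator following the text exactly would withhold the second clamp after a positive test, but would find no sentence on the remaining capsules or on follow-up.

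What is at stake is participant safety. The paired comparison of glucose uptake, its power and its type I error do not depend on this.

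**Working it through.** The protocol gives no figure on this point to reproduce. The check compares sections, with simple arithmetic on dose and timing.

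**1. Dose.** From Aim 1: 500 mg × 2 capsules × 2 per day = 2000 mg/day. Supply: 4 capsules/day × 28 days = 112 capsules, and 112 × 0.5 g = 56 g, dispensed on day 0.

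**2. Dose against the safety statement.** Potential Risks and Protection Against Risk both rest on the absence of reported adverse effects at up to 1000 mg/day. 2000 / 1000 = 2, so the trial dose is twice the level that those statements cover. Potential Risks also notes that supplements can be marketed without formal safety testing. It cites possible estrogenic activity as the reason to exclude a history of ovarian, uterine or breast cancer.

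**3. What the tests cover.** Human Subjects Involvement says that "each subject will participate in two infusion studies with frequent blood glucose monitoring", so the natural reading is one test in the 7 days up to each clamp. This is an assumption.
- First test: day −7 to day 0. Second test: day 21 to day 28.
- Shortest interval: day 0 to day 21 = 21 days. Longest: day −7 to day 28 = 35 days.
- Second test on day 21: the 28 capsules for days 22 to 28 (7 × 4) are still at home, and no rule says to stop them.
- Second test on day 28: the 108 capsules for days 1 to 27 (27 × 4) have already been taken.

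The second test therefore either comes late or comes with capsules left and no instruction. If the testing window refers to entry into the study as a whole, no test after day 0 is assured.

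**4. The reason for the exclusion.** Inclusion of Women attributes the exclusion of pregnancy to a radioactive tracer. Potential Risks says the tracer, D2G, is not radioactive. No section attributes the exclusion to resveratrol.

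**5. Number of women.** 50% of 55 subjects is 27 or 28 women across ages 21 to 65. The documents do not say how many could conceive and give no pregnancy rate, so no expected count is offered.

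**The case against.** The strongest reply is that the exclusion concerns the clamps. The stated reason is the tracer, which is given only there, and tests timed to the clamps fit that reason. No section links resveratrol to harm in pregnancy, and the remark on estrogenic activity is applied only to cancer history. This stands in part: it makes the point precautionary. It does not remove the point, because the exclusion is written for the study and not only for the infusions. The tracer reason is also undercut by the protocol's own description of the tracer.

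A second reply is that much is already handled: pregnant and breast-feeding women are excluded, tests are required within a week, a positive test bars the second clamp, and the principal investigator monitors safety continuously. This also stands. What remains is pregnancy that begins, or first becomes detectable, during one 28-day course.

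A third reply is that the consent form, which was not available for this review, may advise on contraception and on stopping capsules. It may, so a reader should not infer that participants receive no such advice. Eligibility and withdrawal rules nevertheless belong in the protocol body.

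Two further inferences are tempting and unsupported. One is that the pregnancy test is left unscheduled because the screening tests, safety laboratories and visit outline do not name it. Those lists need not be complete, and Study Population and Recruitment gives the window. The other is that the share of dosing days without a listed visit measures the defect. The remedy adds no visit, so that share would not change.

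**Conclusion.** The concern holds as a precautionary safety gap. The protocol excludes pregnancy and tests for it around the clamps, but its body sets no contraception condition and no instruction to stop capsules during 28 days of home dosing at 2000 mg/day. It should be corrected, because the correction is cheap and the protocol's own safety statements stop at half the trial dose.

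The conclusion rests on the protocol body as supplied and on reading the test requirement as one test before each clamp; the entry-only reading would widen the gap. The size of the risk is unknown.

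A reader might infer that resveratrol is known to endanger a pregnancy, or that the trial's results are compromised. The documents support neither. Nor do they support requiring that a woman's contraceptive method stay unchanged between the clamps, since nothing in them makes contraception a source of bias.

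**What to change.** For women of child-bearing potential:

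1. In Study Population and Recruitment and in Human Subject Characteristics, require a negative urine pregnancy test on day 0 before capsules are dispensed, and agreement to effective contraception through the last dose on day 28.
2. In Early Study Termination, beside the drug-screen rule, state that capsules stop at once and that the woman is withdrawn and followed up if pregnancy is suspected or confirmed. Tell her this when the capsules are handed over.
3. Keep the existing test before the second clamp.
4. Check that the consent form says the same.

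Protection during dosing comes from the contraception condition and the stop instruction. The second test only adds a check before the clamp. As an editorial matter, the tracer wording in Inclusion of Women should be brought into line with Potential Risks.

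The cost is a few sentences and a urine test at a visit where urinalysis is already planned. The downside is that a few eligible women may decline.
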